7.1.11. Vital Sign Measurements

Vital sign measurements include blood pressure and pulse rate. Additional measurements may be obtained if clinically indicated. Any value considered clinically significant by the investigator will be recorded as an AE on the CRF. Clinically significant changes compared to baseline values should be followed until clinical resolution.

7.1.12. Physical Examinations

Complete physical examinations include the following body system evaluations: General Appearance, Skin, Musculo-skeletal, Eyes, Ears, Nose, Throat, Cardiovascular, Chest, Abdomen, Lymph Nodes, and Neurological.

Symptom-oriented evaluations will be performed when clinically indicated. Weight will be measured at Screening, Day 1 of each treatment cycle and the End of Study Visit.

7.1.13. Electrocardiograms

12-Lead ECGs will be performed at Screening, Cycle 1, Days 1 and 15, Day 1 of each subsequent cycle, and at End of Study.

7.2. Efficacy Assessments

7.2.1. Criteria for Evaluation of Response and Progression

Evaluation of response to treatment and determination of disease progression in subjects with AML will be evaluated using criteria defined in Revised Recommendations of the International Working Group for Diagnosis, Standardization of Response Criteria, Treatment Outcomes, and Reporting Standards for Therapeutic Trials in Acute Myeloid Leukemia.³⁶ Efficacy assessments for subjects with MDS or CMML will be assessed using the modified International Working Group Response Criteria in Myelodysplasia.³⁷

7.2.2. Disease Response Criteria

7.2.2.1. Subjects with AML

- **Complete Remission (CR)**

The subject must be free of all symptoms related to leukemia and have an absolute neutrophil count $> 1.0 \times 10^9/L$, platelet count $\geq 100 \times 10^9/L$, and normal bone marrow with $< 5\%$ blasts and no Auer rods

- **Complete Remission with Incomplete Blood Count Recovery (CRi)**

As per CR but with residual thrombocytopenia (platelet count $< 100 \times 10^9/L$) or residual neutropenia (absolute neutrophil count $< 1.0 \times 10^9/L$)

- **Partial Remission (PR)**

A $\geq 50\%$ decrease in bone marrow blasts to 5 to 25% abnormal cells in the marrow; or CR with $\leq 5\%$ blasts if Auer rods are present

- **Treatment Failure**

Treatment has failed to achieve CR, CRi, or PR.

- **Recurrence**

Relapse after confirmed CR: reappearance of leukemic blasts in peripheral blood or $\geq 5\%$ blasts in the bone marrow not attributable in the Investigator's opinion to any other cause (e.g., bone marrow regeneration after consolidation therapy) or appearance of new dysplastic changes

7.2.2.2. Subjects with MDS or CMML

- **Complete Remission (CR)**

The subject must be free of all symptoms related to leukemia and have an absolute neutrophil count $\geq 1.0 \times 10^9/L$, platelet count $\geq 100 \times 10^9/L$, bone marrow $\leq 5\%$ myeloblasts, with normal maturation of all cell lines, hemoglobin $\geq 11\text{g/dL}$, and no blasts in the peripheral blood

- **Partial Remission (PR)**

All CR criteria with $\geq 50\%$ decrease in bone marrow blasts over pre-treatment (but still $> 5\%$)

- **Marrow CR**
In bone marrow, $\leq 5\%$ myeloblasts and decrease by $\geq 50\%$ over pre-treatment
- **Hematologic Improvement (HI) (subjects with MDS only)**
 - **Erythroid Response (HI-E)**
 - **Major Response**
 - ◊ For subjects with pretreatment hemoglobin $< 11 \text{ g/dL}$, $> 2 \text{ g/dL}$ increase in hemoglobin
 - ◊ For RBC transfusion-dependent subjects, transfusion independence
 - **Minor Response**
 - ◊ For subjects with pretreatment hemoglobin $< 11 \text{ g/dL}$, 1 to 2 g/dL increase in hemoglobin
 - ◊ For RBC transfusion-dependent subjects, $\geq 50\%$ decrease in transfusion requirements
 - **Platelet Response (HI-P)**
 - **Major Response**
 - ◊ For subjects with a pretreatment platelet count $< 100 \times 10^9/\text{L}$, an absolute increase of $\geq 30 \times 10^9/\text{L}$
 - ◊ For platelet transfusion-dependent subjects, stabilization of platelet transfusion independence
 - **Minor Response**
 - ◊ For subjects with a pretreatment platelet count $< 100 \times 10^9/\text{L}$, a $\geq 50\%$ increase in platelet count with a net increase $> 10 \times 10^9/\text{L}$ but $< 30 \times 10^9/\text{L}$
 - **Neutrophil Response (HI-N)**
 - **Major Response**
 - ◊ For absolute neutrophil count (ANC) $< 1.5 \times 10^9/\text{L}$ before therapy, $\geq 100\%$ increase or an absolute increase of $\geq 0.5 \times 10^9/\text{L}$, whichever is greater
 - **Minor Response**

- ◊ For ANC $< 1.5 \times 10^9/L$ before therapy, ANC $\geq 100\%$, but absolute increase $< 0.5 \times 10^9/L$

- **Progressive Disease**

Subject did not achieve PR, CR or marrow CR or is otherwise a non-responder.

- **Relapse after CR or PR**

One or more of the following:

- Return to pretreatment bone marrow blast percentage
- Decrement of $\geq 50\%$ from maximum remission/response levels in granulocytes or platelets
- Reduction in hemoglobin concentration by ≥ 2 g/dL or transfusion dependence.

- **Progression or Relapse after Hematologic Improvement**

One or more of the following:

- A $\geq 50\%$ decrement from maximum response levels in granulocytes or platelets
- A reduction in hemoglobin concentration by ≥ 2 g/dL
- Transfusion

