1.3.3. Phase 2 Study in Advanced Hematologic Malignancies

A larger Phase 2 study was conducted in patients with advanced hematologic malignancies.⁷ A total of 165 patients were enrolled; 85 had received prior therapy with antimetabolites, including 6-MP or cytosine arabinoside (ara-C). Patients were treated with SM-108 orally, at doses of 70, 200 or 300 mg/m² BID (140, 400 or 600 mg/m²/day). In 39 patients with chronic myelogenous leukemia (CML), 21 had complete responses (CRs) and 6 had PRs for an OR rate of 69%. Among 30 patients with AML, 7 had PRs (23%). Among 36 patients with MDS, 1 had a CR, 12 had PRs for an ORR of 36%. For 13 patients with polycythemia rubra, 4 had CRs and 7 had PRs for an ORR of 84.6%). The RR rate was highest in patients with CML and MDS at doses of \geq 600 mg/m²/day. Clinical responses by dose are described in **Table 1**.

Table 1. Phase 2 Study in Hematologic Malignancies: Clinical Response by Dose

Diagnosis Dose (mg/day)	CML	MDS				Polycythaemia vera	AML	Total (%)
		CMMoL	RAEB	RAEB in T	Total			
< 200			1/2		½		0/2	1/4 (25)
200 to < 400	1/1	1/1	0/1	0/3	1/5	2/2	1/3	5/11 (45.5)
400 to < 600	2/4	0/1	2/7	0/3	2/11	3/3	2/11	9/29 (31)
600 to < 800	20/22	4/7	2/3	2/4	8/14	6/8	2/10	36/54 (66.7)
800 to < 1000	4/11	0/2	0/1	1/1	¼		2/4	7/19 (36.8)
1000 \leq	0/1							0/1
Total (%)	27/39 (69.2)	5/11 (45.5)	5/14 (35.7)	3/11 (27.3)	13/36 (36.1)	11/13 (84.6)	7/30 (23.3)	58/118 (49.1)

The most commonly reported adverse events were gastrointestinal (nausea, anorexia, vomiting, abdominal discomfort; 66%), followed by allergic symptoms (rash, pruritis; 1%). Changes in laboratory values occurred in 30 of 165 (18%) of patients, all were transient/reversible and most were \leq Grade 2. A total of 14 patients (8%) experienced bone marrow suppression (neutropenia, thrombocytopenia, reduced Hb). The nadir was reached in 2 -3 weeks for white blood cell (WBC) count and platelets, 5 weeks for Hb, and recovery from nadir to pre-dose values was approximately 2 weeks (**Table 2**).

Table 2. Phase 2 Study Hematologic Malignancies: Adverse Events in $\geq 2\%$ Patients

Total Number of Patients		165
Number of Patients Reporting (%)	Increased ALT	16 (9.7)
	Nausea	15 (9.1)
	Increased AST	14 (8.5)
	Loss of appetite	11 (6.7)
	Decreased platelet count	8 (4.8)
	Rash	7 (4.2)
	Vomiting	6 (3.6)
	Decreased hemoglobin	4 (2.4)
	Abdominal discomfort	3 (1.8)
	General malaise	3 (1.8)
	Decreased WBC	3 (1.8)
	Increased total bilirubin	3 (1.8)
	Increased GTP	3 (1.8)

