7.2.3. Efficacy Endpoints

7.2.3.1. Primary Efficacy Endpoint

To evaluate the proportion of subjects with objective response achieved within 3 cycles of treatment with FF-10501-01 (i.e., within 3 months) in subjects with relapsed/refractory AML or relapsed/refractory high-risk MDS or CMML.

- **Subjects with AML**

Objective responses for subjects with AML include complete remission (CR), complete remission with incomplete blood count recovery (CRi) and partial remission (PR) as defined above.

- **Subjects with MDS**

Objective responses for subjects with high-risk MDS include complete remission (CR), partial remission (PR), and marrow CR as defined above.

- **Subjects with CMML**

Objective responses for subjects with CMML include complete remission (CR), partial remission (PR) and marrow CR as defined above.

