8.3.2.1. Primary Efficacy Endpoint

The primary efficacy endpoint is the proportion of subjects treated at the MTD in each disease cohort (AML, MDS or CMML) with objective response (OR) within 3 cycles of study drug (i.e., within 3 months). For subjects with AML, OR is CR, CRi, or PR, as defined above. For subjects with MDS or CMML, OR is CR, PR or marrow CR, as defined above. The proportion of subjects in each disease cohort treated at the MTD will be summarized, and 90% confidence intervals will be estimated.

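### As worded, partial remission in MDS/CMML requires marrow blasts both at or below 5% and above 5%, so one component of the primary efficacy endpoint can never be met

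*Protocol*

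**What the plan says.** Protocol 7.2.2.2 sets the response criteria for MDS and CMML. CR requires no disease-related symptoms, recovered neutrophils, platelets and hemoglobin, no blasts in the peripheral blood, and a marrow with at most 5% "myeloblasts, with normal maturation of all cell lines, hemoglobin" at or above its threshold. PR requires every CR criterion plus a reduction of at least 50%, worded as a "decrease in bone marrow blasts over pre-treatment (but still" above 5%). Marrow CR requires at most 5% "myeloblasts and decrease by" at least 50%. Progressive disease is defined by default: "Subject did not achieve PR, CR or marrow CR or is otherwise a non-responder".

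These categories feed the primary efficacy endpoint. Protocol 7.2.3.1 states: "Objective responses for subjects with CMML include complete remission (CR), partial remission (PR) and marrow CR as defined above", with the same components for MDS. Protocol 8.3.2.1 states: "For subjects with MDS or CMML, OR is CR, PR or marrow CR, as defined above". SAP 3.3.1 repeats the endpoint (objective response within three cycles), and the available SAP text does not define PR. Protocol 7.2.1 cites the published International Working Group criteria, but the synopsis and Protocol 3.1 say that a modification of them is used.

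**The concern.** PR takes over all the CR criteria, including the 5% marrow ceiling, and then adds a 5% marrow floor. The authors almost certainly meant the PR marrow clause to replace the CR one, but the text does not say so, and the endpoint sections send the reader back to that text.

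PR is one of three objective-response categories for MDS/CMML, and these are the only diseases in Phase 2a. A response table programmed from the definition would show no PRs, and the response rate would be biased downward. If some assessors follow the evident intention and others the wording, the same record will be scored both ways. Because progressive disease is the default for anyone without CR, PR or marrow CR, an intended PR could also be read as a progression event for PFS.

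**Working it through.** **Inputs.** From Protocol 7.2.2.2, let B be pre-treatment and P post-treatment marrow blast percent, with all non-marrow CR criteria met:

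- CR marrow criterion: P ≤ 5
- PR as written: (P ≤ 5) and (P ≤ 0.5 × B) and (P > 5)
- PR as evidently intended: (P ≤ 0.5 × B) and (P > 5)
- Marrow CR: (P ≤ 5) and (P ≤ 0.5 × B)

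**Logic.** The first and third conditions of PR as written exclude each other, so the set is empty. Enumerating B and P from 0 to 100 in steps of 0.1 gives 0 qualifying pairs as written and 202,500 as intended. None of the intended pairs overlaps marrow CR. Intended PR needs P > 5 and B ≥ 2P, hence B > 10%. Marrow blasts of at least 10% is one of the Phase 2a entry routes in Protocol 4.1, so such subjects belong to the target population.

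**Two hypothetical records.** Assume no disease-related symptoms, normal maturation of all cell lines, ANC 1.5 × 10⁹/L, platelets 120 × 10⁹/L, hemoglobin 11.5 g/dL and no peripheral blasts.

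| Marrow blasts | 50% fall? | As intended | As written |
|---|---|---|---|
| 18% to 8% | yes (8 ≤ 9) | PR | not CR, PR or marrow CR; progressive disease by default |
| 18% to 4% | yes (4 ≤ 9) | CR | CR; not PR because 4 is not above 5 |

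**Effect on the reported rate.** Protocol 8.3.2.1 asks for a proportion with a 90% confidence interval but names no method. I use the exact (Clopper-Pearson) interval with n = 20, the planned Phase 2a size: lower limit = Beta quantile 0.05 with parameters (x, n − x + 1), upper limit = Beta quantile 0.95 with parameters (x + 1, n − x). Each reclassified subject moves the rate by 1/20 = 5 points.

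| Responders | Rate | Exact 90% CI |
|---|---|---|
| 4/20 | 20% | 7.1 to 40.1% |
| 3/20 | 15% | 4.2 to 34.4% |
| 2/20 | 10% | 1.8 to 28.3% |
| 1/20 | 5% | 0.3 to 21.6% |
| 0/20 | 0% | 0 to 13.9% |

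If two of four responders are intended PRs, the reported result drops from the first row to the third.

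**Can PR be the main category?** Protocol 1.3.3 reports for the earlier SM-108 study: "Among 36 patients with MDS, 1 had a CR, 12 had PRs for an ORR of 36" percent. Removing the 12 PRs would turn 13/36 (36.1%) into 1/36 (2.8%). This is illustrative only: that study's PR definition is not given, and some of those patients might be marrow CRs here.

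**The case against.** The strongest reply is that the intention is obvious. The clause requiring blasts still above 5% has no function unless it replaces the CR ceiling, and an experienced assessor would read it that way. The documents do not say that response is derived by algorithm, or who assigns the category; Appendix D describes a general disease response assessment. The realistic outcome is therefore inconsistent classification rather than a certain count of zero. That qualification stands, but it does not rescue the wording. Elsewhere the authors wrote the exception out: CRi for AML (Protocol 7.2.2.1) is CR with a stated departure on counts. Nor can the cited published criteria settle the matter, since the protocol says it modifies them and a reader cannot tell which departures were deliberate.

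A second reply is that CR limits myeloblasts while PR speaks of marrow blasts, so both conditions might hold at once. Table 7 lists a single marrow blast percent, so the listed data cannot separate the two. A subject who did fit would already be a CR.

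Third, the stakes are limited. Safety is the primary objective and response rate a secondary one (Protocol 2.1 and 2.2). No hypothesis test is planned (SAP 2.4.2), and per-subject response listings would let an error be seen. These points are correct. But with no test, the estimate and its interval are the whole efficacy result, and this one is labelled primary.

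Finally, the 5-point step assumes that all 20 subjects are evaluable and pooled. Efficacy uses the per-protocol set by disease cohort (SAP 3.3), so the denominator may be smaller and the step correspondingly larger.

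**Conclusion.** The concern holds. As written, no MDS/CMML subject can be a PR, and an intended PR is scored as a non-responder and falls within the definition of progressive disease. With 20 pooled, evaluable subjects the loss is 5 points for each intended PR. The total cannot be stated, because no expected PR rate is given; it could be nil if no subject with more than 10% baseline marrow blasts reaches the intended category. The conclusion rests on reading the definition literally and on treating myeloblasts and marrow blasts as the one variable collected. AML is unaffected. The definition should be corrected before response is assigned or programmed.

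**What to change.** In Protocol 7.2.2.2 replace the MDS/CMML PR entry with: *all CR criteria except the marrow-blast criterion, with marrow blasts decreased by at least 50% from pre-treatment but still above 5%.* Restate it in SAP 3.3.1 and build the response table from that text. Check any MDS/CMML response already recorded against it.

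This makes the category attainable and keeps it separate from CR and marrow CR. It also takes these subjects out of the default progressive-disease definition, which at present conflicts with Protocol 3.1, where responders continue until progression; those passages should be reconciled.

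The cost is one sentence in each document, with no new data and no additional subjects.

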Partial remissions have occurred in 3 AML patients (50, 100 and 400 mg/m² BID) after 1 – 3 cycles, lasting for at least 28, 5 and 6 cycles, respectively. A total of 8/25 (32%) AML patients, including the 3 PRs, have attained stable disease control with no disease progression over 4 – 28 cycles. A marrow complete response was achieved in 1 MDS patient treated at 400 mg/m² BID x 14 days after 1 cycle and was sustained for 14 cycles. A major platelet response was observed in 1 patient treated at 400 mg/m² BID x 21 days, sustained for 1 cycle. Four of 8 MDS patients (50%), including the marrow CR, attained stable disease control with no disease progression over 3, 5, 14 and 17 cycles, respectively.

FF-10501-01 was rapidly absorbed with mean T_{max} of 2.74 hours and mean $t_{1/2}$ of 4.05 hours. Drug exposure (AUC_{0-24} and AUC_{course}) increased with dose in a near linear manner.

Potent suppression of circulating xanthosine monophosphate (XMP), a marker of IMPDH activity, has been observed following FF-10501-01 administration on Day 1 of Cycles 1 and 2 at doses $\geq 50 \text{ mg/m}^2 \text{ BID}$.

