During the study, a Safety Review Committee, consisting of the actively recruiting investigators, the Medical Monitor, and FPHU, will review data from each cohort on an ongoing basis.

Subjects on the 21-day schedule will receive FF-10501-01 on a BID schedule. For all subjects on the 21-day dosing schedules, blood samples for pharmacokinetic assessment of FF-10501 and M1 in plasma will be collected on Cycle 1 Day 1 pre-dose (any time), between 0.5-1 hr post-dose, and between 2-4 hr post-dose, and Day 15 pre-dose (within 15 minutes prior to dosing), between 0.5-1 hr post-dose, and between 2-4 hr post-dose.

Blood concentration of xanthosine monophosphate (XMP) will be assessed as a pharmacodynamic endpoint.

For subjects on the 21-day dosing schedules, blood samples for XMP assessment will be collected on Cycle 1 Day 1 pre-dose (any time), between 0.5-1 hr post-dose, and between 2-4 hr post-dose, and Day 15 pre-dose (within 15 minutes prior to dosing), between 0.5-1 hr post-dose, and between 2-4 hr post-dose.

Disease assessments, including analysis of blood and bone marrow aspirates, will be performed at the end of Cycle 1 and Cycle 3 and every 2 cycles thereafter. Disease assessments may be performed at other time points at the discretion of the investigator.

Subjects who demonstrate objective response (OR) or stable disease (SD) will be allowed to continue therapy with FF-10501-01 until progression of disease, observation of unacceptable adverse events, intercurrent illness or changes in the subject's condition that prevents further study participation.

Blood for hematology, platelet and serum chemistry determinations will be collected within 28 days of Cycle 1 Day 1, on Days 1, 8, 15, and 22 of Cycle 1, on Day 1 of each subsequent cycle, and at the End of Study Visit. Urine will be collected for urinalysis within 28 days of Cycle 1, on Day 1 of each subsequent cycle and at the End of Study Visit.

Safety will be assessed through the monitoring of adverse events (AEs), clinical laboratory parameters (hematology, serum chemistry), vital sign measurements, electrocardiograms (ECGs) and physical examinations. Adverse events will be classified according to the Medical Dictionary for Regulatory Affairs (MedDRA) and graded according to the National Cancer Institute Common Terminology Criteria for Adverse Events (NCI CTCAE) version 4.03.

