1.3.2. Selection and Timing of Doses

For all subject cohorts, if 1 of 3 subjects per cohort experiences DLT, the cohort will be expanded to 6. If 2 of 6 subjects per cohort experience DLT, all further dose escalation will

stop. If 0 of 3 or \leq 1 of 6 subjects per cohort experience DLT by Day 28 following dosing of FF-10501-01, dose escalation will proceed to the next cohort. At the MTD of 400 mg/m² BID, the longest schedule of administration below the schedule of administration eliciting DLT will be declared the recommended Phase 2 dose (RP2D) and schedule. A total of 6 subjects will be treated at the RP2D and schedule. No intra-subject dose escalation will be allowed from previous dose levels/schedules of administration until at least one subject has completed Cycle 1 at the longer schedule of administration (e.g., 21 or 28 days) with no Grade 2 or greater toxicities observed. Additionally, patients currently on study will have the option to extend their current dosing schedule to 21 days, followed by 7 days off, repeated every 28 days (=1 cycle), or 28 days of continuous dosing, whichever is chosen as the best schedule, if seen in the patient's best interest by the principal investigator. Dose level adjustments for DLT will be made. Subjects who experience DLT at the first dose level, 50 mg/m² BID, will not be dose-reduced. Up to 48 subjects are planned for Phase 1.

Subjects on the 21-day schedule will receive FF-10501-01 on a BID schedule. For all subjects on the 21-day dosing schedules, blood samples for pharmacokinetic assessment of FF-10501 and M1 in plasma will be collected on Cycle 1 Day 1 pre-dose (any time), between 0.5-1 hr post-dose, and between 2-4 hr post-dose, and Day 15 pre-dose (within 15 minutes prior to dosing), between 0.5-1 hr post-dose, and between 2-4 hr post-dose.

Subjects who demonstrate objective response (OR) or stable disease (SD) will be allowed to continue therapy with FF-10501-01 until progression of disease, observation of unacceptable adverse events, intercurrent illness or changes in the subject's condition that prevents further study participation.

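### The MDS/CMML criterion for Progressive Disease describes non-response, and loss of response is not tied to PFS, so the PFS event is not consistently defined

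*Protocol*

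**What the plan says.** **MDS and CMML.** Protocol 7.2.2.2 gives Progressive Disease as "Subject did not achieve PR, CR or marrow CR or is otherwise a non-responder". It names no change from baseline, no threshold and no time point. Stable disease is not among its categories.

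**AML.** Protocol 7.2.2.1 describes the same idea, "Treatment has failed to achieve CR, CRi, or PR", but labels it Treatment Failure.

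**Stable disease elsewhere.** Protocol 3.1 states: "Subjects who demonstrate objective response (OR) or stable disease (SD) will be allowed to continue therapy with FF-10501-01 until progression of disease". SAP 1.1 and SAP 1.3.2 repeat the rule. Protocol 1.7.2 reports: "Four of 8 MDS patients (50%), including the marrow CR, attained stable disease control with no disease progression".

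**Loss of response.** For MDS/CMML there are two rules, one for relapse after CR or PR and one for progression or relapse after hematologic improvement (HI). HI is defined for MDS only. Neither rule names marrow CR, which Protocol 7.2.3.1 and 8.3.2.1 count as an objective response. For AML, Recurrence covers relapse after CR.

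**PFS.** Protocol 7.2.3.2, Protocol 8.3.2.2 and SAP 3.3.2 run PFS from first dose to the earlier of death and the first objective sign of progression. None refers to a particular criterion in 7.2.2, and none mentions relapse.

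**Source standard.** Protocol 7.2.1 cites published response criteria. Protocol 3.1 calls the criteria in use a modification of them, and 7.2.2 prints its own text. No order of precedence is given.

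**The concern.** The only printed definition carrying the label Progressive Disease for MDS/CMML is a definition of not responding. A subject cannot be both stable, and so entitled to continue until progression, and already progressed for want of a remission. One analyst following the printed label and another following the interim reporting practice would give the same stable subject different PFS times, and the SAP does not choose between them.

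The opposite problem arises for responders. A subject who reaches marrow CR and then loses it meets no printed loss criterion. Even where a relapse rule exists, nothing says that relapse ends PFS.

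The whole Phase 2a cohort is MDS/CMML. PFS is a secondary objective with planned Kaplan-Meier curves, medians and 90% confidence intervals.

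**Working it through.** No design figure depends on the PFS definition, so there is no planned number to reproduce. The check sets the texts side by side and then counts the interim cases.

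**Step 1. Printed criteria compared (Protocol 7.2.2.1 and 7.2.2.2).**

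| Situation | AML | MDS/CMML |
|---|---|---|
| No remission reached | Treatment Failure | Progressive Disease |
| Stable disease | not defined | not defined |
| Worsening with no prior response | no criterion | no criterion |
| Loss of CR | Recurrence | relapse rule |
| Loss of PR | none | relapse rule |
| Loss of CRi (AML) or marrow CR (MDS/CMML) | none | none |
| Loss of HI | HI not defined | post-HI rule (MDS only) |

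The same outcome has a neutral label in one disease group and a progression label in the other. True worsening without a prior response has no criterion in either.

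**Step 2. Effect on the reported MDS subjects (Protocol 1.7.2).** Inputs: 8 MDS subjects, 4 reported without progression, 1 of these 4 the marrow CR.

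- As reported: 4/8 = 50% without progression.
- Non-remitters among the four: 4 − 1 = 3.
- Under the printed line these 3 are Progressive Disease, which leaves 1/8 = 12.5%.

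The four durations are 3, 5, 14 and 17 cycles, and the marrow CR was sustained for 14. If that subject is the one at 14 cycles, the three reclassified subjects were stable for 3, 5 and 17 cycles.

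**Step 3. Allowance for HI.** The post-HI rule can be read to displace the Progressive Disease line for an MDS subject with HI only. Best responses of the three are not given. The report adds that "A major platelet response was observed in 1 patient", without stating the disease; HI is defined for MDS only. If that subject is one of the three, the count is 2/8 = 25%, and each further HI-only subject among them adds one. CMML has no HI category, so this reading is not open there.

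**Step 4. The AML counterpart.** The same section says: "A total of 8/25 (32%) AML patients, including the 3 PRs, have attained stable disease control with no disease progression". Non-remitters: 8 − 3 = 5. These 5 are Treatment Failure and not progression by label, while the 3 MDS non-remitters in the same position are Progressive Disease. The 3 PRs are the only AML objective responses reported, and Recurrence does not cover loss of PR.

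**Step 5. What a literal median would measure.** If every subject without a response is an event at the visit where non-response is called, and nobody is censored earlier, then S(visit) is at most responders/n. With n = 20 and 9 or fewer responders, S is at most 9/20 = 0.45, so the median falls no later than that visit. It would reflect the assessment schedule and not the disease. The documents give no assumed Phase 2a response rate, so this is a conditional statement only.

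**Step 6. From relapse to PFS.** None of the three PFS passages mentions relapse. Adding marrow CR to the relapse rule would therefore not by itself make its loss a PFS event; a second sentence is needed.

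**The case against.** The strongest reply is that nobody would apply the line literally. PFS requires objective evidence of progression, and failing to remit is hard to call that. The line sits under response criteria, while 7.2.1, which covers response and progression, points to a published standard. The continuation rule ("Subjects who demonstrate objective response (OR) or stable disease (SD) will be allowed to continue therapy") and the interim report both treat stable disease as separate. This stands as far as likely practice goes: the documents show the sponsor reporting stable subjects as not progressed. It does not settle the text. The protocol prints its own version, calls its criteria a modification and does not say which governs. Analysts who disregard the printed label are then using an unwritten rule in an unblinded trial.

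A second reply is that the standard cited in 7.2.1 may define stable disease and progression fully. That is possible, and a reader should not infer that PFS has no definition anywhere. Its contents are outside the documents, however, and the printed line conflicts with the stable-disease wording whatever the standard says.

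A reader might also infer that the non-progressor count certainly falls from 4 to 1 of 8, or that the fault is confined to MDS/CMML. The first ignores the HI reading and the unreported best responses. The second overlooks AML, which lacks a progression criterion for non-remitters and a loss rule for CRi and PR.

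**Conclusion.** The printed MDS/CMML progression line is wrong as written for PFS: followed literally, it turns stable subjects into events. Loss of marrow CR has no criterion, relapse is not linked to PFS in either document, and AML has a related gap. This should be corrected before PFS is derived.

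On the interim counts, the share of MDS subjects without progression would go from 4/8 to 1/8, or to 2/8 or more under the HI reading. This assumes that the marrow CR is the only CR, PR or marrow CR among the four, as reported. The counts pool Phase 1 doses and schedules and do not predict the Phase 2a cohort.

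The reach is limited. A reader might infer that the response results, survival, safety or the right to stay on drug are compromised. The documents do not support that. Objective response within 3 cycles, overall survival and the safety summaries do not use this line, stable subjects are expressly allowed to continue, and SAP 2.4.2 plans no formal hypothesis test. Nor is there evidence that any subject has been coded as progressed for failing to respond.

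**What to change.** 1. Protocol 7.2.2.2: rename the MDS/CMML line No response, and state that it is not a PFS event.
2. Define stable disease as no CR, PR or marrow CR, for MDS also no HI, and no progression.
3. State in Protocol 7.2.1 and SAP 3.3.2 that the progression criteria of the standards cited in 7.2.1 govern PFS for both MDS/CMML and AML, and take precedence over the printed text where they differ. The sponsor should confirm that those standards cover worsening in subjects who never responded.
4. Extend the MDS/CMML relapse rule to marrow CR; its marrow-blast limb fits best, because marrow CR is defined on marrow blasts alone. Extend AML Recurrence to CRi and PR. For AML PR the printed limit of 5% marrow blasts cannot be carried over unchanged, since PR itself allows 5 to 25%. A limit from the cited standard, or return to the pretreatment percentage as in the MDS rule, would serve.
5. State in SAP 3.3.2 that relapse or loss of response counts as progression for PFS, dated at the first assessment showing it.

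New numerical progression thresholds are not needed if the cited criteria are adopted.

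Cost: protocol and SAP wording, and derivation of progression dates from data already collected (marrow blasts, hematology, transfusions). This assumes that the cited criteria need nothing beyond those data.
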